1 STUDY SYNOPSIS

Sponsor / Sponsor-Investigator	[name]. med. [name]
Study Title	Patients with Esophageal Carcinoma undergoing Minimally Invasive Ivor Lewis Esophagectomy with or without intraoperative Endoscopic Pylorus Balloon Dilatation: A Randomized Controlled Trial Investigating the Benefits of Intraoperative endoscopic Pylorus Dilatation
Short Title / Study ID	WIDE Trial
Protocol Version and Date	Version 1.3 (18.12.2025)
Study Registration	The study will be registered at www.clinicaltrials.gov and on the Swiss National Clinical Trials Portal (SNCTP) at www.kofam.ch .
Study Category and Rationale	Clinical trial project category A This is a clinical trial investigating the addition of a commonly used intervention to a standard operation in patients undergoing minimally invasive surgical therapy due to esophageal cancer.
Background and Rationale	For esophageal carcinoma, minimally invasive thoraco-abdominal resection is the standard therapy in a curative setting. Delayed gastric conduit emptying (DGCE) is reported in up to 40% of patients after esophageal resection, making it a significant problem in their treatment. DGCE prolongs recovery and hospital stay which in turn increases the overall costs. DGCE or gastroparesis refers to the stomach's inability to empty its contents into the small intestine in a normal timeframe postoperatively. Mechanical stretching of the pylorus has been shown to reduce the incidence of DGCE in retrospective studies. In open surgery, pylorus dilatation was often performed. However, in the era of minimally invasive surgery, mechanical stretching of the pylorus is technically not possible as in open surgery. There is a need for more and stronger evidence to investigate whether mechanical stretching of the pylorus improves the postoperative course of the patients and lowers the postoperative complication rates.

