Number of Participants with Rationale	Our hypothesis is that intraoperative endoscopic balloon dilatation of the Pylorus reduces the incidence of DGCE. According to our calculation of the required study size for a power of 80%, we need 52 included patients per study arm. To account for potential dropouts or loss to follow-up, an estimated attrition rate of 10% was considered. Consequently, the final target enrolment is increased to 58 patients per group, leading to a total of 116 patients.
Study Intervention	For patients in the intervention group, a balloon catheter will be inserted orally by experienced gastroenterologists under endoscopic control. The pylorus is then dilated to a predetermined size of 30mm using a standard balloon dilatation kit. The intervention will be performed before the gastric conduit is formed.
Study procedures	All patients are treated according to our internal guidelines for esophageal surgery. Baseline data is collected preoperatively. The relevant information concerning the postoperative course of each patient is retrieved from the specific patient charts. These data are collected by ward physicians who do not have access to the study documents and therefore do not know to which group the patients were randomized. After 5- and 10-days, the output of the nasogastric tube will be assessed. Additionally, a radiological X-Ray to assess the width of the gastric tube will be performed. After 3 months patients are asked to fill out the DGCE symptom questionnaire and EORTC QLQ-OES18 questionnaire for a more detailed assessment concerning DGCE specific symptoms and general GI Symptoms and quality of life. Additionally, a radiological passage will be performed after 3 months.
Study Duration and Schedule	December 2025 - June 2028 all patients included and operated. Follow up for 3 months after last operation to assess late DGCE and QoL.
Investigator(s)	
[name], [name]. med. Clarunis University Digestive Health Care Center [name] phone: mail: [contact]
 
[name], PD Dr. med. Clarunis University Digestive Health Care Center [name] phone: [name] mail: [contact]
 
[name], med. pract. Clarunis University Digestive Health Care Center [name] phone: [name] mail: [contact]

Study Center(s)	Clarunis University Digestive Healthcare Centre

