Men are more frequently affected by esophageal cancer than women. The risk of developing esophageal cancer increases with age. Radical surgical removal of esophageal carcinomas is the only curative therapy available today, especially in EAC. However, the operation is associated with high postoperative morbidity and a high complication rate and a 90-day mortality rate of around 4% (17). Thoracoabdominal resection with creation of a gastric tube or, if possible, transhiatal resection are currently the standard operations for esophageal carcinomas (16). Some of the most important postoperative complications after esophagectomy are anastomotic leak, pulmonary complications such as pneumonia and chylothorax, as well as delayed gastric conduit emptying (DGCE) and dysphagia. DGCE refers to impaired or slowed passage of gastric contents through the conduit, leading to prolonged gastric retention after esophagectomy. It causes symptoms such as nausea, vomiting, regurgitation and inability to tolerate oral intake. DGCE is described in up to 40 percent of patients after esophagectomy and therefore presents a great burden in these patients (8,9). The DGCE can put mental and physical stress on these patients. Also, DGCE may increase the risk of anastomotic leaks through the increased pull on the new esophago-gastric anastomosis. Due to the prolonged recovery, the time until discharge from the hospital and start of rehabilitation is significantly delayed as a result of DGCE. The DGCE also results in higher costs which place an additional burden on the healthcare system.

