There are various accepted definitions of DGCE. In 2020, a study involving 33 experts in the field of esophageal surgery attempted to develop a universally applicable definition (10). In the study, the experts defined criteria for early DGCE (<14 days postoperatively) as follows: >500 mL daily nasogastric tube output measured on the morning of post-operative day 5 or later, or >100% increase in gastric tube width on frontal chest x-ray along with the presence of an air-fluid level. Experts describe the following parameters for the presence of late DGCE (>14 days postoperatively): The patient should have at least two of the following symptoms: early satiety/fullness, vomiting, nausea, regurgitation or inability to meet caloric needs by oral intake, and delayed contrast passage on upper gastrointestinal radiograph or timed barium swallow. Furthermore, we learned from this study, that the DGCE syndrome can be defined on the basis of the occurrence of symptoms such as nausea or vomiting. In addition, clinical parameters such as the length of time the gastric tube is in place and the flow rate of the gastric tube as well as radiological parameters can be used as diagnostic tools. The DGCE is associated with the gastric tube remaining in place for a longer period of time. In addition, an increased risk for anastomotic leakage and aspiration is described (17). Various techniques for reducing DGCE have been investigated in the past. In former times, surgical pylorus drainage in the form of pyloroplasty or pyloromyotomy was often a standard procedure for distal esophageal resection. In the era of open surgery, the pylorus was often mechanically dilated using regular forceps, this cannot be done in minimally invasive surgery. Since the widespread adoption of minimal invasive surgery, however, these interventions have been performed less frequently. Another technique that was used was the intraoperative injection of Botox into the pylorus. However, this technique did

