3.2 Primary and secondary endpoints

The Primary outcome is defined as incidence of early DGCE. Early DGCE is defined as presence of a nasogastric tube with an output of >500ml on day 5 or later and/or >100 % increased gastric tube width on radiological chest X-Ray on

day 5 or later (in comparison with baseline X-Ray upon admission on the ICU). DGCE will be diagnosed using both of these mentioned radiological and clinical tools on day 5 and 10 (10).

As secondary endpoints we define the incidence of late DGCE measured using the symptom orientated DGCE questionnaire and a radiological passage examination after 3 months. Furthermore, we want to investigate potential differences between the two groups concerning the rate of anastomotic leaks, postoperative complications such as pneumonia, duration until first bowel movement after surgery, duration until first intake of solid food, presence of vomiting during the postoperative course and length of hospital stay. In addition, we will analyze the quality of life via symptom orientated questionnaires after 3 months using the EORTC QLQ-OES18 questionnaire.

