5 STATISTICS AND METHODOLOGY

5.1. Statistical analysis plan and sample size calculation

The aim of this power analysis was to calculate the minimum required sample size for our randomized controlled trial (RCT) investigating the effect of intraoperative endoscopic pyloric dilatation on the incidence of early delayed gastric conduit emptying (DGCE) within the first 14 days after esophagectomy.

The sample size calculation for this study was based on findings from Boshier et al. (18), which demonstrated a reduction in the incidence of DGCE from 48% to 22% following intraoperative pyloric stretching procedures. To achieve a statistical power of 80% ($1 - \beta = 0.80$) while maintaining a Type I error rate of 0.05 ($\alpha = 0.05$), a power analysis for comparing two independent proportions was performed. The absolute difference in proportions (Δ) was set at 26 (0.48

- 0.22). Using these parameters, the required sample size was calculated to be 52 patients per group, resulting in a total of 104 patients for the study. This ensures sufficient power to detect a statistically significant difference in DGCE incidence between the two treatment groups.

To account for potential dropouts or loss to follow-up, an estimated attrition rate of 10% was considered. Consequently, the final target enrolment is increased to 58 patients per group, leading to a total of 116 patients. This adjustment maintains adequate statistical power even if a subset of participants does not complete the study.

The statistical analysis will be conducted according to the intention-to-treat (ITT) principle. Categorical variables will be analyzed using Chi-square or Fisher's exact test, while continuous variables will be evaluated using either independent t-tests or Mann-Whitney U tests, depending on the distribution. Multivariable logistic regression analysis will be used to adjust for relevant covariates and potential confounding factors.

All statistical analyses will be performed in collaboration with an experienced statistician from our research group using validated software such as SPSS or R. A significance level of $p < 0.05$ will be considered statistically significant for all tests.

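### Does planning on a 48% control rate, when the protocol's background gives up to 40%, undermine the stated 80% power?

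*Protocol*

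**What the plan says.** Section 5.1 rests the sample size on a single cited study of pyloric stretching, which "demonstrated a reduction in the incidence of DGCE from 48% to 22% following intraoperative pyloric stretching procedures". It fixes the absolute difference at 26 points, alpha at 0.05 and power at 80%, arrives at 52 per group, and adds 10% attrition to reach 58 per group (116 in all). It then concludes: "This ensures sufficient power to detect a statistically significant difference in DGCE incidence between the two treatment groups". The Synopsis repeats the result: "According to our calculation of the required study size for a power of 80%, we need 52 included patients per study arm".

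Elsewhere the protocol gives a lower figure for the same complication. Section 2 says "DGCE is described in up to 40 percent of patients after esophagectomy", and the Synopsis says that it "is reported in up to 40% of patients after esophageal resection". Section 2 also notes: "There are various accepted definitions of DGCE". Section 3.2 sets the trial's own rule. It begins "Early DGCE is defined as presence of a nasogastric tube with an output of" more than 500 ml on day 5 or later, and adds, joined by and/or, a more than 100% increase in gastric tube width on chest X-ray.

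For the analysis, section 5.1 says "Categorical variables will be analyzed using Chi-square or" Fisher's exact test. The Synopsis mentions only chi-square.

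**The concern.** The planning control rate lies 8 points above the highest figure that the protocol gives for DGCE after esophagectomy, and the document does not say why. It does not state which definition lies behind the 48% or the 40%, whether either matches the endpoint in section 3.2, or what the centre's own rate is. A control rate taken too high is a familiar way for a trial to end up underpowered. If the true rate is nearer 40% and the benefit shrinks with it, the chance of missing a real effect could be well above the planned 20%, although section 5.1 presents the power as secured. The open choice between chi-square and Fisher's exact test adds to the worry, because Fisher's test has less power at this sample size.

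**Working it through.** **Inputs.** From section 5.1: p1 = 0.48, p2 = 0.22, alpha 0.05, power 0.80, attrition 10%. From section 3.3: 1:1 allocation. From the Synopsis and section 2: a background rate of up to 0.40. A two-sided test is an assumption, since the protocol does not state it. It reproduces 52, whereas a one-sided test would give 41.

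**The plan's own figure.** With pooled variance and no continuity correction, and p̄ the mean of p1 and p2,

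n = [1.960·√(2p̄(1−p̄)) + 0.842·√(p1(1−p1) + p2(1−p2))]² / (p1−p2)²

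Here p̄ = 0.35, so n = [1.960·√0.455 + 0.842·√0.4212]² / 0.26² = (1.322 + 0.546)² / 0.0676 = 51.6, which rounds up to 52. Attrition: 52/0.9 = 57.8, which rounds up to 58. Both stated figures are reproduced.

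**Carrying the effect over to a 40% control rate.** The cited effect can be transferred in different ways:

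- same absolute difference: 0.40 − 0.26 = 0.14
- same relative reduction: 0.40 × 0.22/0.48 = 0.183
- same treated rate: 0.22

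Power by full enumeration of the two binomial outcomes, for the uncorrected chi-square test:

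| Control v treated | Difference | Power, 52/arm | Power, 58/arm | n/arm for 80% (formula) |
|---|---|---|---|---|
| 48% v 22% (plan) | 26 points | 81.2% | 84.5% | 52 |
| 40% v 14% | 26 points | 87.0% | 90.2% | 45 |
| 40% v 18.3% | 21.7 points | 69.8% | 74.3% | 68 |
| 40% v 22% | 18 points | 51.9% | 56.2% | 103 |

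The normal approximation at 52 per arm gives 80.3%, 85.8%, 68.6% and 51.0%, within about 1.2 points of the enumeration. A fourth route, keeping the odds ratio (40% v 16.9%), gives 74.9% by the normal approximation. At a 40% control rate, the smallest difference with 80% power at 52 per arm is 24.0 points.

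At a fixed difference, power rises as the control rate falls from 48% to 40%, because the variances get smaller. It drops below 80% only when the difference itself drops below 24 points.

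**Choice of test.** At 48% v 22%, Fisher's exact test has 74.7% power at 52 per arm and 79.7% at 58. The usual reason to prefer it is small expected counts, which do not arise here: under the plan the expected number of events is 52 × 0.35 = 18.2 per arm, and for 40% v 14% it is 52 × 0.27 = 14.0. An analyst working from section 5.1 would use chi-square for the primary endpoint. Naming the uncorrected test in advance is not free either, since its actual type I error at 52 per arm is 6.2% near a 48% null rate.

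**The case for a change.** The strongest case for a change is that one document gives two rates for the complication on which its size depends, offers no reason for using the higher one, and then states the power confidently. Even if all 58 per arm are evaluable, power stays below 80% at a 40% control rate when either the relative reduction or the 22% treated rate carries over. Since 40% is described as an upper figure, the true rate could be lower still: at 30% with the same relative reduction, power is about 52% at 52 per arm by the normal approximation. A constant relative reduction is a reasonable way to carry an effect across baseline rates.

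Much of this stands as description. The gap is unexplained, and 52% to 87% is not a bound on what could happen. It does not show that a stated figure is wrong. The power sentence follows directly from the inputs listed just before it and is read with them. The 40% comes with no definition and no account of how the pylorus was managed, whereas 48% is the comparison rate of one study of pyloric stretching. A higher rate is also plausible under an and/or rule with scheduled X-rays. Whether the definitions match depends on sources that are not at hand. The low end of the power range requires an 18-point effect that the protocol nowhere assumes, and any trial loses power when its effect is smaller than planned. A reader of a non-significant result would in any case look to the observed difference and its confidence interval rather than to a table of planning scenarios.

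**Conclusion.** No change follows. The 52 and 58 per arm and the 80% power are correct for the inputs that section 5.1 names. The tension with the background figure is a missing explanation, not an error in the design. At a 40% control rate with 52 evaluable per arm, power is 87%, 70% or 52% depending on whether the absolute difference, the relative reduction or the treated rate is assumed to hold. Only the first of these keeps the difference that the protocol set, and there power exceeds the target. These figures assume a two-sided 5% uncorrected chi-square test and equal arms.

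A sentence on why 48% is expected under the section 3.2 definition would help a reader, but enrolment, endpoint and analysis would all stay as they are. A sensitivity table would correct nothing that is stated. The test choice is one that analysts would settle the same way at these cell counts.

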After inclusion into the study, baseline data will be collected and stored in a study-specific Redcap Database. This Redcap Database fulfills all regulations for a study database. In a next step after the operation, surgery-specific data is collected and stored into the redcap database. The surgical reports will not show whether a patient has received an intervention or not. The relevant information concerning the postoperative course of each patient are retrieved from the specific patient charts. These data are collected by ward physicians who do not have access to the study documents and therefore do not know which group the patients were randomized into. After 5 and 10 days, a radiological X-ray of the chest is performed to assess the width of the gastric tube. After 5 and 10 days we also assess whether a nasogastric

tube is in place and, if so, how high the output of the nasogastric tube is. After 3 months we assess the DGCE specific symptoms using the DGCE symptom orientated questionnaire. We also perform a radiological swallow study to record signs, such as delayed contrast passage for late DGCE. Additionally, patients are asked to fill out the EORTC QLQ-OES18 questionnaire to have a more detailed assessment concerning general GI symptoms.

Safety and Unblinding

In case of adverse events, unblinding will be permissible, and procedures for revealing a participant's allocated intervention will be allowed during the trial, also in case of suspension or premature study termination. Unblinding is done by the Surgeon who attended the operation and is therefore not blinded to the group assignment.

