Appendix 1: Schedule of assessments

Study Periods	Screening		In-hospital			Follow up
Days	-X	-14	0	5	10	3 months
Patient Information and Informed Consent		+				
Demographics	X	X				
Medical History	X	X				
In- /Exclusion Criteria	+	+				
Physical Examination	X	X	X	X	X	X
Vital Signs			X	X	X	X
Randomisation		+				
Surgery			X			
Primary Outcome				+	+	
Output Nasogastric tube				X	X	
Radiological passage						+
Radiological Chest X-Ray			X	+	+	
Secondary Outcomes				X	X	X
Adverse Events			X	X	X	X
Quality of life (EORTC QLQ-OES18)		+				+
DGCE Questionnaire		+		+	+	+

Symbol explanations:

X: Routine Examinations in all Esophagectomy patients

+: Study specific/additional Examinations

WIDE TRIAL - CONSORT Flowchart

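### The pre-surgery QLQ-OES18 score is scheduled but has no stated use in the treatment comparison; adjusting for it costs almost nothing and may give a modest gain in precision

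*Protocol*

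**What the plan says.** **Schedule.** In Appendix 1 the row "Quality of life (EORTC QLQ-OES18" carries the study-specific mark at day -14 and at 3 months. Under the legend, patients complete the pre-surgery form only because they are in the trial.

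**Endpoint.** Section 3.2 says "we will analyze the quality of life via symptom orientated questionnaires after 3 months using the EORTC QLQ-OES18 questionnaire". It mentions neither a baseline score nor a change from baseline. Section 3.1 states the aim of analysing whether quality of life improves with dilatation.

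**Analysis.** Section 5.1 says "continuous variables will be evaluated using either independent t-tests or Mann-Whitney U tests, depending on the distribution"; the synopsis gives the same tests. The only provision for adjustment is "Multivariable logistic regression analysis will be used to adjust for relevant covariates and potential confounding factors".

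**Body text on baseline data.** The synopsis says "Baseline data is collected preoperatively" and section 3.3 says "After inclusion into the study, baseline data will be collected and stored in a study-specific Redcap Database". Neither sentence names a questionnaire. The synopsis and sections 3.2, 3.3 and 4.3 name the QLQ-OES18 only in connection with the postoperative assessments. Section 4.3, having just named both questionnaires, gives their time points as days 5 and 10 and 3 months. Appendix 1 places only the DGCE questionnaire on days 5 and 10.

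**The concern.** A baseline measurement of the same scale is usually the most useful covariate for a later score. Here patients are asked for it as a trial-specific burden, yet the analysis text gives it no role in the treatment comparison. Logistic regression could take it in only if the 3-month score were dichotomised, which discards information.

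The trial was sized for a binary primary endpoint, so the quality-of-life comparison gets whatever precision 116 patients happen to provide. If the baseline predicts the 3-month score at all well, ignoring it gives a wider interval than necessary on an outcome that the protocol names among its aims. With no use stated, it also stays open whether a 3-month comparison, a change score or an adjusted model will be reported.

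A practical risk comes with this: if staff work from the body text, which never mentions the day -14 form, the form may not be completed.

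**Working it through.** **1. The plan's own figure.** Section 5.1 gives 48% against 22%, alpha 0.05 and power 80%. Taken as two-sided, with pooled proportion 0.35:

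n = [1.960·√(2·0.35·0.65) + 0.8416·√(0.48·0.52 + 0.22·0.78)]² / 0.26² = (1.322 + 0.546)² / 0.0676 ≈ 51.6, so 52 per group; 52/0.90 = 57.8, so 58.

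Both figures reproduce. They concern the primary endpoint; the protocol states no figure for the QLQ-OES18.

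**2. Completers.** Section 5.1 says "an estimated attrition rate of 10% was considered": 58 × 0.90 = 52.2, so 52 per arm. Section 2 gives "a 90-day mortality rate of around 4" per cent; if deaths come on top of that attrition, 58 × 0.96 × 0.90 = 50.1.

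**3. Detectable difference, unadjusted.** With 52 per arm and 80% power: (1.960 + 0.8416) × √(2/52) = 0.549 SD.

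**4. Effect of adjustment, against the t-test.** The ratio of confidence interval widths, adjusted to unadjusted, is √[(1 − r²)(1 + 1/(N − 4))], where N = 104 and the second factor (1.01) charges the cost of estimating the slope. Equivalent extra patients = 1/ratio² − 1. The correlation r is an assumption, shown as a range.

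| r | Width ratio | Change in width | Detectable difference (SD) | Equivalent extra patients |
|---|---|---|---|---|
| 0 | 1.005 | +0.5% | 0.552 | none |
| 0.1 | 1.000 | 0% | 0.549 | none |
| 0.2 | 0.985 | −1.5% | 0.541 | 3% |
| 0.3 | 0.959 | −4.1% | 0.527 | 9% |
| 0.5 | 0.870 | −13.0% | 0.478 | 32% |
| 0.6 | 0.804 | −19.6% | 0.442 | 55% |

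A simulation of 20,000 trials gave the same width ratios. The number of completers hardly matters: from 45 to 58 per arm the narrowing is 4.0–4.2% at r=0.3 and 12.9–13.0% at r=0.5.

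**5. Change score.** Its width relative to the unadjusted 3-month score is √[2(1 − r)]. At r=0.3 this is √1.4 = 1.183, or 18% wider; at r=0.5 it is 1.00. Apart from the roughly 0.5% cost of estimating the slope, it never beats adjustment, because 2(1 − r) − (1 − r²) = (1 − r)² ≥ 0.

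**6. Where section 5.1 would choose Mann-Whitney.** The table does not cover this case, so it was simulated: 52 per arm, a latent shift of 0.55 SD, and log-normal scores as an assumed example of strong skew.

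| Latent r | Mann-Whitney | Linear regression, robust errors | Baseline-adjusted rank analysis |
|---|---|---|---|
| 0.3 | 78% power | 62% | 81% |
| 0.5 | 78% power | 69% | 88% |

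For such scores, linear regression with robust errors has less power than the protocol's own test. A baseline-adjusted rank analysis does not.

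**The case against.** **Nothing is invalid, and detail may belong in a SAP.** Randomisation makes the unadjusted comparison unbiased, and covariates for a secondary endpoint are often settled in a separate plan, which may exist. The first part stands in full. The second stands only in part: section 5.1 is itself headed as the statistical analysis plan and names unadjusted tests for all continuous variables, so an adjusted analysis would depart from its text.

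**A reader might infer that the baseline score will go unused.** The documents do not support that. Nothing excludes describing baseline balance, and a change score would itself be a continuous variable under section 5.1. What can be said is that no use in the treatment comparison is stated.

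**A reader might infer a sure gain whenever r exceeds about 0.1.** That break-even holds against the t-test only. Section 5.1 moves to Mann-Whitney for unsuitable distributions, and there linear regression can lose power well above r=0.1 (step 6). This objection stands, and it determines the form of the fix.

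**The gain may be small.** An esophagectomy lies between the two measurements, and tumour symptoms before surgery may say little about conduit symptoms afterwards. This stands too: equivalents of 32% or 55% more patients need r of 0.5 or 0.6, for which the protocol offers no evidence.

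**The baseline form rests on one table cell.** True. The general sentences on baseline data do not confirm it, which is why the time points need reconciling.

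**Conclusion.** The point holds as a modest, low-cost improvement to the analysis of one secondary endpoint. A pre-surgery QLQ-OES18 is scheduled, only unadjusted tests are named for continuous outcomes, and the one adjusted model named does not fit the score.

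The loss is one of precision, not bias. Against the t-test, with an assumed 52 completers per arm, adjustment ranges from an interval 0.5% wider (r=0) through 4% narrower (r=0.3) to 13% narrower (r=0.5). It is small below r=0.3 and material from about 0.5; no particular gain should be promised. For skewed scores the gain depends on using a rank-based or ordinal model, and the supporting power figures rest on assumed distributions.

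The primary analysis and the enrolment of 116 do not change.

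**What to change.** **Section 5.1.** State that each 3-month QLQ-OES18 scale is compared between arms with the day -14 score of the same scale as covariate:

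- by linear regression, reporting the adjusted mean difference with 95% confidence interval, where a t-test would have been used;
- by a baseline-adjusted rank-based or ordinal (proportional-odds) model where the distribution would have led to Mann-Whitney.

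Linear regression with robust errors should not stand in for the second, and a change-score t-test should not be used for either.

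**Section 4.3.** Reconcile the questionnaire time points with Appendix 1. Name the day -14 form, since the adjustment depends on its being completed, and say whether the QLQ-OES18 or only the DGCE questionnaire is filled in on days 5 and 10.

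**Cost.** A short addition to section 5.1 and one clarified sentence in section 4.3. No further patients or visits are needed, and no further forms provided that Appendix 1 is followed. The statistical price is one degree of freedom, about 0.5% of interval width if the baseline proves uninformative.
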